#### **3.4.5.2 Laboratory Data**

Laboratory test results include clinical chemistry, hematology, and urinalysis. Continuous lab data, including actual values and changes from baseline, will be summarized using descriptive statistics (including mean, standard deviation, quartiles, median, minima and maxima) for chemistry and hematology parameters. If the scheduled assessment is missing, use the recheck measurement closest in time to scheduled visit (if available).

If a Day 1 laboratory collection occurred after the first dose of study drug, that lab value should not be used as the baseline lab value. The baseline lab value is the last laboratory value collected before study drug administration.

Shift tables will be provided to assess changes from normal to abnormal shifts from baseline to Week 16 for chemistry and hematology parameters.

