9.1.2. Management of Elevated Transaminase Levels (ALT and/or AST)

Nearly all instances of elevated transaminases are expected to be asymptomatic. Check transaminase levels (as well as total bilirubin (TBL), GGT, alkaline phosphatase (ALP), and International Normalized Ratio (INR) within 48-72 hours during an unscheduled visit if the following occurs:

- ALT or AST levels > 3X ULN

Repeat testing every 72 to 96 hours until transaminase levels are below three times the ULN for at least one week or the patient withdraws consent.

Discontinue study drug administration permanently if any of the following occurs:

- ALT or AST > 8X ULN
- ALT or AST > 5X ULN for more than 2 weeks
- ALT or AST > 3X ULN and [TBL > 2 x ULN **or** INR > 1.5]
- ALT or AST > 3X ULN with the appearance of fatigue, nausea, vomiting, right upper quadrant pain or tenderness, fever, rash, and/or eosinophilia (> 5%); The hepatobiliary tree must be visualized (e.g., ultrasound, MRI) and assessed if a patient discontinues taking study drug secondary to elevated transaminase levels. Additional tests/studies may be warranted depending on the clinical presentation.

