### 3.3 Analysis of Treatment Group Comparability

Demographic information (age, sex, ethnicity, race), baseline characteristics (baseline BMI, weight) and baseline disease characteristics (including PAH classification and details, time since diagnosis, baseline PAH concomitant medications, thromboembolic disease assessment, pulmonary function testing, oxygen use during 6MWTs and available baseline right heart catheterization data) will be summarized by treatment arm for all randomized patients.

Descriptive baseline summaries of continuous data will present the group mean, standard deviation, median, minima, and maxima. Descriptive summaries of discrete data will present the category counts as frequencies and percentages.

Unless otherwise stated, the baseline value of any variable will be defined as the last available value recorded prior to the first administration of bardoxolone methyl/placebo. Missing values will not be imputed, unless otherwise noted, and will be tabulated as missing.

### 3.4 Analysis of Part 1

Part 1 data will be analyzed using the analysis populations defined in [Section 3.1](#). Separate analyses will be performed by each cohort. Part 1 analyses will only include data from the placebo controlled portion of the study. If a subject does not complete Part 1, or chooses not to enter Part 2, then all their data will be used in Part 1. If a subject enters Part 2, then all data up to and including the Week 16 visit will be included in Part 1.

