### 3.4.5 Safety Analysis

Safety data will be summarized using the safety population. Missing data will not be imputed for safety analyses. With the exception of adverse events, safety results will be summarized by the CRF nominal study visits (i.e., Week 1, Week 2, Week 4, Week 8, Week 12, and Week 16). For subjects that prematurely discontinue treatment before Week 16 with an End of Treatment (EOT) assessment, that EOT will be used in analysis for the nominal protocol visit most closely matching the subject's visit schedule. Similarly, for patients with safety results at an unscheduled visit that unscheduled visit will be used in analysis for the nominal protocol visit most closely matching the subject's visit schedule. For all safety listings except adverse events, if a safety result does not fall within a scheduled visit window, that result will be included in the safety listings but not the safety table summaries.

Moreover, if retest values are available, all safety analyses should use the results closest to the target study day (e.g., Day 28 for Week 4, Day 56 for Week 8, etc.). If two values are equidistant from the target study day, the earliest of those values will be used in all safety analyses.

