#### **3.4.5.3 Estimated Glomerular Filtration Rate**

For calculation of the eGFR, the 4-variable MDRD equation must be used. The equation is as follows:

$$\text{eGFR} = 175 \times \text{standardized serum creatinine (mg/dL)}^{-1.154} \times \text{age}^{-0.203} \times 1.212 [\text{if black}] \times 0.742 [\text{if female}]$$

The patient's age utilized in the eGFR calculation will be the age by visit listed in the laboratory dataset.

For the eGFR analysis, the value closest to the target study day should be used (Section 3.7.2). Patients randomized to placebo and converted to bardoxolone methyl in Part 2 should use the Week 16 eGFR value as baseline.

The eGFR analyses will not include eGFR values  $\geq 14$  days after the patient's last dose of bardoxolone methyl or placebo.

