### 3.4.5.6 24 Hour Ambulatory Blood Pressure Monitoring

Systolic blood pressure, diastolic blood pressure, pulse pressure and heart rate are collected during the 24-hour ambulatory blood pressure monitoring (ABPM) [REDACTED]. Actual values and changes from baseline values for these four parameters will be summarized using descriptive statistics (including mean, standard deviation, quartiles, median, minima, maxima, and 95% confidence interval) by treatment group at all scheduled study visits. If the scheduled assessment is missing, the recheck measurement closest in time to scheduled visit will be used (if available).

The overall (24 hour) mean for each measure, the day time mean, and the night time mean will be summarized. Appendix A provides more detail of the planned analyses of the 24-hour ABPM data.

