**Table 2. Visit Windows for Unscheduled and End of Treatment Visits in Part 1**

Analysis Visit	Study Day	Analysis Window
Day 1	1	$\text{Study Day} \leq 1$
Week 1	7	$2 \leq \text{Study Day} \leq 10$
Week 2	14	$11 \leq \text{Study Day} \leq 20$
Week 4	28	$21 \leq \text{Study Day} \leq 42$
Week 8	56	$43 \leq \text{Study Day} \leq 70$
Week 12	84	$71 \leq \text{Study Day} \leq 98$
Week 16	112	$99 \leq \text{Study Day} \leq 119$

Records from unscheduled or end of treatment visits that do not fall within an analysis window will be listed, but will not be analyzed. Per Section 3.4.4, for the 6MWT analysis, if use of the visit windows yields more than one value for a particular visit, the average of the two or more values will be used for analysis. For all other analyses, including the eGFR and safety analyses, the value closest to the target study day should be used (Table 2).

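### Outside eGFR, no by-visit safety summary limits days since last dose, so retests after withdrawal for ALT/AST can be tabulated off drug at a later nominal visit

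*SAP*

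**What the plan says.** **The one last-dose limit.** SAP 3.4.5.3: "The eGFR analyses will not include eGFR values" obtained 14 or more days after the last dose of bardoxolone methyl or placebo.

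**Everything else by visit.** SAP 3.4.5.2 (laboratory) states: "If the scheduled assessment is missing, use the recheck measurement closest in time to scheduled visit (if available"). The same rule is given for vital signs and weight (3.4.5.5) and ECG (3.4.5.7). For ABPM (3.4.5.6), "the recheck measurement closest in time to scheduled visit will be used (if available"). None of these refers to the date of last dose.

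**Visit assignment.** Under SAP 3.4.5, for a patient with a result at an unscheduled visit, "that unscheduled visit will be used in analysis for the nominal protocol visit most closely matching" the patient's schedule. The end-of-treatment (EOT) result is handled the same way. The section adds that "if retest values are available, all safety analyses should use the results closest to the target study day", with ties going to the earlier value. Table 2 (SAP 3.7.4) gives the windows in study days from Day 1; results outside them are listed only. For patients who do not complete Part 1 or do not enter Part 2, SAP 3.4 says "then all their data will be used in Part 1".

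**Where off-drug values come from.** Protocol 8.4 requires withdrawal at specified ALT/AST levels. Protocol 9.1.2 says: "Repeat testing every 72 to 96 hours until transaminase levels are below three times the ULN for at least one week", or until consent is withdrawn.

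**What is tabulated.** The Part 1 shift table for chemistry and hematology runs from baseline to Week 16 (SAP 3.4.5.2). No table of worst post-baseline values appears in the visible Part 1 safety text.

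**The concern.** A patient who stops drug has no later scheduled on-drug samples. The SAP's rules then look for the nearest unscheduled or recheck value, and the only test it must pass is a window counted from Day 1. That window cannot tell a value on drug from one taken weeks after stopping.

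For transaminases the protocol itself produces such values, and it does so in the patients who left because of the laboratory abnormality. The retests follow the recovery. If a recovered value is tabulated at a later visit, the bardoxolone column contains a result that does not describe exposure to bardoxolone. More transaminase withdrawals are to be expected on active drug (Protocol 5.1.3 reports rises in almost all treated patients), so the tendency is to make the arms look more alike.

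This matters because SAP 1.5.2 rests the dose-range recommendation on a judgement of acceptable safety profiles.

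**Working it through.** There is no plan figure to reproduce; this is a check of what the stated rules select.

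**Inputs from the documents**
- Windows and targets (Table 2): Week 4, Days 21–42 (target 28); Week 8, Days 43–70 (56); Week 12, Days 71–98 (84); Week 16, Days 99–119 (112).
- Retests every 3 or 4 days until ALT/AST have been below 3X ULN for at least 7 days (Protocol 9.1.2).
- Selection: value closest to the target day, ties to the earlier (SAP 3.4.5).

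**Assumptions**
- Last dose and EOT fall on the same day, L.
- T, the days off drug until ALT is below 3X ULN, is not in the documents. I take 3 to 28 days.

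**Worked case.** L = 88, T = 14. Retests every 3 days fall on Days 91, 94, 97, 100, 103, 106, 109 and 112. The first at least 14 days off drug is Day 103, and 103 + 7 = 110, so the last retest is Day 112. With 4-day spacing the last is also Day 112. That value is on target, is selected as Week 16, and is 112 − 88 = 24 days off drug. It appears as normal if it is at or below ULN. The EOT value on Day 88 belongs to the Week 12 window; if a scheduled Week 12 sample was taken nearer Day 84, that one is used and the EOT value is only listed.

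**Range of L.** A retest reaches the Week 16 window if L ≥ 99 − (off-drug day of last retest). The upper end is the last L for which the selected value is still 14 or more days off drug.

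| T (days, assumed) | Last retest, days off drug (3-day / 4-day spacing) | Week 16 value is ≥14 days off drug for L (3-day) | (4-day) |
|---|---|---|---|
| 3 | 12 / 12 | none | none |
| 7 | 18 / 16 | 81–98 | 83–97 |
| 14 | 24 / 24 | 75–98 | 75–97 |
| 21 | 30 / 32 | 69–98 | 67–97 |
| 28 | 39 / 36 | 60–98 | 63–97 |

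**Displacement within a window.** L = 99, T = 14, 3-day spacing: the EOT value (Day 99) is 13 days from target and the Day 111 retest is 1 day from it. Day 111, 12 days off drug, is chosen over the EOT value.

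**Earlier withdrawals.** With T from 14 to 28 and 4-day spacing, retesting ends on Day 52–64 for L = 28, Day 66–78 for L = 42 and Day 80–92 for L = 56. None reaches Day 99, so Week 16 is missing and the off-drug values go to earlier cells. Example: L = 42, T = 14, 3-day spacing gives a retest on Day 57, which is 1 day from the Week 8 target and 15 days off drug.

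**Effect of extending the eGFR rule.** The Week 16 window opens on Day 99, and 99 − 14 = 85, so no Week 16 value could come from a patient with last dose on or before Day 85. For L = 88, the Day 112 value would go, but the Day 100 retest (12 days off drug) would then fill the cell.

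**The case against.** The case against is substantial.

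- **Nominal visits, not on-treatment visits.** The SAP speaks of nominal visits. Summarising patients by calendar visit whatever their drug status is a legitimate choice, and a narrower rule for eGFR is not in itself a contradiction. This stands. But the SAP gives no reason for confining the limit to eGFR, and its reader cannot tell which tabulated values are off drug.
- **The late case is unusual.** Protocol 5.1.3 puts transaminase peaks two to four weeks after starting or increasing the dose, and the only Part 1 escalation in Cohorts 3 and 4 is at Week 4. Withdrawal near Day 84 is off that pattern. This stands: Weeks 4, 8 and 12 are the likelier cells.
- **A final retest need not be normal.** Retesting may stop after a week below 3X ULN, which can still be above ULN. This stands.
- **The signal survives elsewhere.** The EOT value is tabulated at an earlier visit (with maxima reported) or listed; clinically significant laboratory changes are adverse events (Protocol 11.6); termination reasons are summarised (SAP 3.2). This stands, and it rules out reading the rule as concealing the event.
- **Mean ALT may move little.** Most rises resolved on continued drug within two weeks of the peak (Protocol 5.1.3), so on-drug late means may be near baseline anyway. This stands.

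A reader might also infer three stronger points that the documents do not support. First, that eGFR is discarded while creatinine from the same transaminase retest is kept: the 9.1.2 panel is transaminases, total bilirubin, GGT, alkaline phosphatase and INR, with no creatinine, magnesium, weight or blood pressure. Second, that the four-week Follow-up visit lands in the Week 16 cell: the SAP assigns Follow-up to no Table 2 window, and including all of a patient's data in Part 1 does not assign it to a visit. Third, a percentage dilution of mean changes: no document gives the off-drug share of values at any visit.

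**Conclusion.** The gap is real. Only eGFR has a last-dose limit; laboratory, vital signs and weight, ECG and ABPM summaries have none, and the Table 2 windows do not supply one. For transaminases the protocol's own retesting can put an off-drug value into a later nominal visit. The other parameters are exposed only if an unscheduled measurement happens to be made.

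The Week 16 shift cell can be filled by a retest 14 or more days off drug for last doses on about Day 60–98 at the slowest assumed recovery (28 days), narrowing to about Day 81–98 at 7 days, and not at all at 3 days. These ranges rest on the assumed recovery time and on retesting as prescribed.

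The number of patients affected and the shift in any summary cannot be derived. The nearest figure is the 4 to 11% of patients with rises above 3X ULN in earlier studies (Protocol 5.1.3), and withdrawal requires more than that. The point is worth correcting because the visible Part 1 shift table looks only at Week 16 and because the SAP already contains the kind of rule that is missing. Mock tables, which are not among the documents, might include a worst-value display; the SAP text does not promise one.

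**What to change.** 1. In SAP 3.4.5, state one last-dose cut-off for all by-visit safety summaries and shift tables, in Parts 1 and 2. The existing eGFR rule would serve: values 14 or more days after last dose are left out of nominal-visit summaries and shown in a separate post-treatment row. The sponsor should choose the number of days and state the reason.
2. Add a shift table from baseline to worst on-treatment value for chemistry and hematology, with on-treatment defined in days from last dose. The cut-off alone is not enough: it still admits values 1 to 13 days off drug, and where it does act it turns a normal Week 16 cell into a missing one, so the abnormality still does not appear there.
3. Say how the Follow-up visit is handled in by-visit tables.

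The cost is slightly fewer values at late visits and a little extra programming. No new data are needed.

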#### **3.4.5.3 Estimated Glomerular Filtration Rate**

For calculation of the eGFR, the 4-variable MDRD equation must be used. The equation is as follows:

$$\text{eGFR} = 175 \times \text{standardized serum creatinine (mg/dL)}^{-1.154} \times \text{age}^{-0.203} \times 1.212 [\text{if black}] \times 0.742 [\text{if female}]$$

The patient's age utilized in the eGFR calculation will be the age by visit listed in the laboratory dataset.

For the eGFR analysis, the value closest to the target study day should be used (Section 3.7.2). Patients randomized to placebo and converted to bardoxolone methyl in Part 2 should use the Week 16 eGFR value as baseline.

The eGFR analyses will not include eGFR values  $\geq 14$  days after the patient's last dose of bardoxolone methyl or placebo.

#### **3.4.5.4 Physical Exam Data**

Physical examination data is collected as normal/abnormal categories at each time point by body system. Abnormal physical examinations will be listed by patient, body system and visit.

#### **3.4.5.5 Vital Sign Measurement**

Vital sign measurements include patient's heart rate, respiration rate, and temperature, weight, BMI, and blood pressure (systolic and diastolic). Actual values and changes from baseline values for vital signs and weight will be summarized using descriptive statistics (including mean, standard deviation, quartiles, median, minima and maxima) by treatment group at all scheduled study visits. If the scheduled assessment is missing, use the recheck measurement closest in time to scheduled visit (if available).

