5.1.2. Fluid Overload

Similar to ERAs in certain patient populations, including bosentan in advanced congestive heart failure and avosentan in advanced CKD, bardoxolone methyl treatment was found to be associated with an increased risk for fluid overload and heart failure hospitalizations in the BEACON trial, which enrolled patients with Stage 4 CKD (eGFR 15-29 mL/min/1.73 m²) and type 2 diabetes. The overall increased risk for fluid overload and heart failure events with bardoxolone methyl appeared to be limited to the first three to four weeks after initiation of treatment. Elevated BNP and prior hospitalization for heart failure were identified as risk factors that contributed to increased risk for these events. The increased risk for these events from bardoxolone methyl treatment had not been observed in six previous CKD studies, which were mostly conducted in patients with Stage 3b CKD (eGFR 30-44 mL/min/1.73 m²), patients with hepatic dysfunction, cancer patients, or healthy volunteers.

Review of admission notes and narrative descriptions for heart failure hospitalizations in BEACON indicates that heart failure in bardoxolone methyl-treated patients was often preceded by rapid fluid weight gain (several kilograms within the first weeks of treatment initiation) and was not associated with acute renal decompensation or acutely reduced left ventricular contractility. Available data from BEACON and other studies suggest that bardoxolone methyl treatment can differentially affect hemodynamic status according to the clinical condition of patients and likely promotes fluid retention in patients with more advanced renal dysfunction and other recognized risk factors associated with heart failure at baseline. This current study will employ risk mitigation procedures to reduce the potential for bardoxolone methyl-induced fluid overload, including exclusion of patients with the identified risk factors and close monitoring for fluid retention within the first month of treatment.

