5.1.5. Weight Loss

Decreases in weight and reports of anorexia/decreased appetite have been observed following treatment with bardoxolone methyl in patients with CKD and type 2 diabetes. In the studies of patients with CKD and type 2 diabetes, 17% of bardoxolone methyl patients reported the adverse events of weight decrease or decreased appetite (irrespective of relationship to treatment). Weight reduction was more pronounced in patients treated with bardoxolone methyl than in those given placebo.

Weight loss of approximately one kilogram per month was observed, with patients of higher body-mass index at baseline losing more than those of normal or moderately-elevated body-mass index. Patients who reported taste-related adverse events had more weight loss.

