^a Total screening period should not exceed 60 days. If screening is longer than 28 days, BNP should be repeated through the central lab prior to randomization.

^b Study Day 1 is the day of administration of the first dose. **On Study Day 1, all procedures should be performed before study drug administration.**

^c Under the delegation of the Investigator and following Sponsor prior approval for each visit, a patient may be seen by a home health professional, qualified by documented training to perform study-specific procedures. If the visit is completed by home health professional, a limited physical assessment directed to assess for fluid retention and clinical worsening will be performed under the delegation of the Investigator

^d Patients who discontinue from the study prior to the Week 16 study visit will need to be brought back for all early termination assessments (i.e., both an end-of-treatment visit and then a follow-up visit 4 weeks after the date of administration of the last dose of study drug). Patients should complete the end-of-treatment procedures, including the 6MWT, prior to any adjustments being made to their PAH treatment regimen.

^e Screen A eligibility procedures do not need to be repeated on Day 1; however, a review of any changes in eligibility criteria should be evaluated prior to Day 1 procedures, and a urine pregnancy test should be performed for WOCBP.

- ^f Weights taken at home by the patient will begin on Day 2 and should be taken daily for the first 8 weeks and weekly thereafter, preferably at the same time each day and must be recorded in a diary and reviewed with the coordinator during telephone contacts and office visits.
- ^g If clinical worsening is suspected, further clinical evaluations may be required per Section 9.10.32.
- ^h A serum pregnancy test will be performed at Screen A for WOCBP or at any point in time if a pregnancy is suspected. All other pregnancy assessments will be urine pregnancy tests. Additional pregnancy assessments will be performed more frequently if required by local law or requested by local regulatory authorities or IRBs/ECs.
- ⁱ AE assessments on Day 1 should be done following study drug administration.

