9.1.1. Management of Fluid Status

Specific risk mitigation procedures will be employed to reduce the potential for bardoxolone methyl-induced fluid overload. These procedures include exclusion of patients with any clinically significant renal disease, defined as an eGFR value of < 45 mL/min/1.73 m². To exclude patients with significant cardiac dysfunction, the study will exclude patients with a history of left-sided heart disease. Patients who have evidence of volume overload at baseline, defined as BNP level of > 400 pg/mL, will also be excluded. Laboratory data will also be used to monitor fluid status after randomization.

Additionally, after randomization patients will be closely monitored for rapid weight gain suggestive of fluid overload. Patients will be given a Sponsor-provided scale to use at home to collect and record their weights daily during the first 4 weeks (Cohorts 1 and 2) or 8 weeks (Cohorts 3 and 4) of the treatment period and weekly thereafter. Patients who experience a five-pound (2.3 kilogram) or greater increase in weight since their Day 1 weight during Part 1 and during the first 4 weeks (Cohorts 1 and 2) or 8 weeks (Cohorts 3 and 4) of Part 2 will be instructed to stop taking their study medication immediately and return to the clinic for an unscheduled physical examination and laboratory assessment by the Investigator. Patients may not restart their study medication until the Investigator has completed and documented an assessment of fluid overload.

Investigators should also advise patients to watch for signs and symptoms of fluid overload. Patients should be informed to notify their physicians immediately if they experience swollen feet, chest pain, and shortness of breath with mild exertion or while lying down, or other relevant symptoms. The Investigator should immediately assess symptoms of fluid overload and determine appropriate medical management, as necessary, including whether stopping drug administration is required. At the earliest sign of worsening or new onset peripheral edema or other signs and symptoms of acute volume overload, Investigators will also be expected to determine if changes to a patient's diuretic regimen is needed.

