9.10.8. Weight and Body Mass Index (BMI)

Weight should be measured at the times indicated in [Table 3](#) or [Table 4](#) and [Table 5](#) or [Table 6](#). Body mass index (BMI) will be calculated in the eCRF each time the weight is recorded. The Sponsor will provide each patient with a scale to use at home to capture daily weights. Weights should be taken at the same time each day and recorded in a patient diary. During the first four weeks (Cohort 1 and 2) or first eight weeks (Cohort 3 and 4) of both Part 1 and Part 2, weights will be collected daily; weekly weights will be collected thereafter. Patients will be instructed to stop administering study drug and contact the Investigator if their daily weight increases as per the criteria outlined in Section 9.1.1. Patients will be provided instructions within the Informed Consent Form to help ensure consistent weight collection throughout the study.

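### Weight is tabulated only at scheduled visits, and no specified table counts patients who reach the protocol's own 2.3 kg weight-gain criterion

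*SAP*

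**What the plan says.** **Collection and trigger.** Protocol 9.1.1 sets the criterion: "Patients who experience a five-pound (2.3 kilogram) or greater increase in weight since their Day 1 weight during Part 1". Such patients "will be instructed to stop taking their study medication immediately and return to the clinic for an unscheduled physical examination". They may restart once the investigator has documented a fluid assessment. Protocol 9.10.8 supplies the means: "The Sponsor will provide each patient with a scale to use at home to capture daily weights". In Cohorts 3 and 4 the home weights "will begin on Day 2 and should be taken daily for the first 8 weeks and weekly thereafter" (Protocol 7.5, notes to Table 4). In Cohorts 1 and 2 the daily period is four weeks.

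**Analysis.** SAP 3.4.5.5 states: "Actual values and changes from baseline values for vital signs and weight will be summarized using descriptive statistics". The statistics are mean, SD, quartiles, median, minimum and maximum, by treatment group at scheduled visits. A recheck is used when the scheduled value is missing. SAP 3.4.5 takes Weeks 1, 2, 4, 8, 12 and 16 as the visits and attaches unscheduled results to the nearest one, but "if retest values are available, all safety analyses should use the results closest to the target study day". SAP 3.7.4 (Table 2) gives the windows. SAP 3.7.2 treats the Week 6 visit as unscheduled, because not every protocol version has it.

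**Opposing effect.** Protocol 5.1.5 reports, for chronic kidney disease with type 2 diabetes: "Weight loss of approximately one kilogram per month was observed". Protocol 9.1.4 says a similar loss may occur in this trial.

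The visible SAP text does not mention home weights or the 2.3 kg criterion.

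**The concern.** Protocol 5.1.2 explains why weight is watched: in an earlier trial in advanced kidney disease, heart failure on this drug often followed a gain of several kilograms in the first weeks. The relevant event is therefore a rapid rise in an individual patient, possibly between visits and possibly reversed once drug is stopped or diuretics are given. The planned tables describe the distribution of weight on six fixed occasions. They do not answer how many patients in each arm met the protocol's own criterion. SAP 1.5.2 rests the dose-range recommendation partly on doses having an acceptable safety profile, so that count bears on the primary objective.

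**Working it through.** **1. The plan's own figure.** 5 lb × 0.45359 = 2.268 kg, which rounds to the stated 2.3 kg.

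**2. Which weights reach the table.** Scheduled visits fall within ±3 days of target (Protocol 7.5).
- *Trigger visit on Day 18.* The Week 2 window is Days 11 to 20, target Day 14. Day 18 is 4 days from target. An on-time scheduled weight is at most 3 days away, so it is kept and the trigger weight is dropped. An unscheduled weight nearer the target than the scheduled one could win under 3.4.5, but the recheck rule in 3.4.5.5 would use it only if the scheduled weight were missing.
- *Week 6 in Cohorts 3 and 4.* Table 4 of the protocol schedules a clinic weight at Day 42±3 (Days 39 to 45), two weeks after the Week 4 escalation. Days 39 to 42 fall in the Week 4 window (21 to 42), 11 to 14 days from target. Days 43 to 45 fall in the Week 8 window (43 to 70), 11 to 13 days from target. An on-time Week 4 or Week 8 weight always displaces it.

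**3. Data collected against data summarised.** Home weights in Part 1: Cohorts 3 and 4, Days 2 to 56 daily plus 8 weekly = 55 + 8 = 63; Cohorts 1 and 2, 27 + 12 = 39. Post-baseline visits summarised: 6.

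**4. Capture by scheduled visits.** Assume onset uniform over Days 2 to 28 (26 days), visits on target, and a gain lasting D days. It is seen if a visit falls between onset and onset + D.
- D = 3: (3 + 3 + 3)/26 = 35%
- D = 7: (5 + 7 + 7)/26 = 73%
- D = 14: (5 + 7 + 14)/26 = 100%

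The durations are assumptions; the documents give none.

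**5. Offset in the mean, if the gain is still present at the visit.** If a share p gains g kg and the rest lose L kg, the mean is zero at p = L/(L + g). At 1 kg/month, L is 0.23, 0.46 and 0.92 kg at Weeks 1, 2 and 4.

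| | Week 1 | Week 2 | Week 4 |
|---|---|---|---|
| g = 2.3 kg | 9% | 17% | 29% |
| g = 4 kg | 5% | 10% | 19% |

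At Week 4 with g = 2.3 kg, p is 17% for a loss of 0.5 kg/month and 38% for 1.5 kg/month.

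**6. One subcohort.** About 24 patients at 2:1 gives 16 active. Suppose 3 are up 2.3 kg and 13 are losing 1 kg/month.
- Mean at Week 1: (3×2.3 − 13×0.23)/16 = +0.24 kg
- Mean at Week 2: (3×2.3 − 13×0.46)/16 = +0.06 kg
- Mean at Week 4: (3×2.3 − 13×0.92)/16 = −0.32 kg

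The maximum would read +2.3 kg, but it would read the same with 1 gainer or 4. A count would read 3/16 = 18.75% whatever the others lost.

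Steps 4 and 5 describe different situations: in one the gain has gone by the visit, in the other it is still there. They should not be added together.

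**The case against.** A reader might infer that weight is summarised only as change and that fluid gain reaches no summary table. The documents do not support either reading.
- Actual values are tabulated too. A gain present at a scheduled visit appears in the maximum and, if common enough, in the upper quartile. It also widens the SD: in the subcohort above, by the mixture alone, to 3.22 × √(3/16 × 13/16) = 1.26 kg.
- A patient who reaches the trigger on Day 24 and leaves without a Week 4 visit has that weight carried into Week 4.
- Adverse events by preferred term and severity (SAP 3.4.5.1), reasons for termination (SAP 3.2) and newly started medications, which would include a new diuretic (SAP 3.4.3), are all shown by arm.
- The safety committee reviews weights, BNP and fluid-related events (Protocol 9.6.3), unblinded (SAP 2.2).
- By-patient listings of all eCRF and external data are planned (SAP 2.3).

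These points stand and limit the concern. They do not supply the missing count. Adverse-event tables depend on an investigator recording an event, and the visible text defines no fluid-related grouping of terms. A patient who interrupts briefly and restarts need not appear among terminations. Exposure (SAP 3.4.2) runs to the Week 16 visit and does not subtract interruptions. Listings and committee review are not reported comparisons between arms.

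It is also fair that a 2.3 kg gain is a screening trigger, not a diagnosis of fluid overload, and that many home readings per patient will produce some false exceedances in both arms. That argues for keeping home and clinic weights apart.

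**Conclusion.** The gap is real but narrow. As specified, the weight tables can miss short gains between visits, and they discard a clinic weight taken two weeks after dose escalation in Cohorts 3 and 4. No specified table gives the number of patients meeting the protocol's criterion or interrupting drug because of it. Other tables may carry part of the signal.

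A reader might go further and infer that the tables would show reassuring weight loss while many patients retain fluid. That is not established. The offset affects the mean and not the maximum. It is only about 0.2 to 0.5 kg in Weeks 1 and 2. It borrows a loss rate from kidney disease with type 2 diabetes, and the shares of gainers are illustrative. The supported statement is that the mean is a poor signal for this risk.

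The conclusion rests on the visible text. The mock tables and the safety committee plan, which the SAP mentions, are not among the documents and could hold a threshold table.

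**What to change.** Add to SAP 3.4.5.5, by arm for Part 1:
- number and percent of patients with any post-baseline gain of at least 2.3 kg from Day 1, using all clinic weights (scheduled, Week 6 and unscheduled);
- the same count from home-diary weights, shown separately, if those weights are in the database;
- maximum gain, day of first occurrence and number of weight-triggered interruptions;
- an exact 95% confidence interval for the difference, in the pooled Part 1 comparison.

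Keep the existing descriptive statistics.

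For Part 2, give descriptive counts only, since Appendix B of the SAP rules out inferential statistics there. Two inconsistencies must be reconciled before this is programmed. Protocol 9.1.1 can be read as taking Day 1 as the reference weight in Part 2, but later in the same section takes Week 16. The notes to protocol Table 6 end daily weighing at Week 20 in Cohorts 3 and 4, while 9.1.1 and 9.10.8 give eight weeks.

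The cost is one or two tables and a check on whether diary weights are databased, which the documents do not say. No new procedure is needed. Home readings will add scale and day-to-day noise in both arms. Intervals would be wide in a subcohort of about 16 against 8, so the pooled comparison should carry them.
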